7.3 Visit 3 – 30-day Follow-up

Visit 3 occurs 30 days (-7 to +14 days) after the ablation procedure. The subject will visit the study site for the following assessments:

- Document any changes or updates to the subject's relevant concomitant medications (blood thinning/anticoagulants, antiplatelets, opioids, systemic chemotherapy, systemic steroids, immunotherapies, anti-inflammatories, NSAIDs, antibiotics, and medications used to treat adverse events)
- Document any changes or updates to the subject's concomitant procedures.
- Complete two validated quality of life questionnaires: EORTC QLQ-C30 and the lung-specific QLQ-LC13. These questionnaires should be administered in person, during the study visit. However, they may be administered over the phone, when needed.
- Collect key vitals: blood pressure, heart rate, and pulse oximetry.
- Evaluate ECOG performance status.
- Evaluate Technique Efficacy, defined as ablation of the target tumor(s) with the ablation zone completely overlapping or encompassing the entire target tumor(s) using **CT imaging** at 30 days (-7 to +14 days) post the original ablation procedure.
- Record readmission to any hospital for any unplanned reason within 30 days of the ablation. The Investigator will assess the reason for the admission and capture the reason in the clinical database.
- Record any applicable AEs or SAEs:
 - If within 30 days of the ablation procedure, record any AEs or SAEs that may have occurred since the last study visit.
 - If after 30 days of the ablation procedure, record only device- or procedure-related AEs or any SAEs that may have occurred since the last study visit.

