The number and percentage of subjects experiencing perioperative AEs (time of consent through 30 days of any ablation procedure), device- and procedure-related AEs (30 days post any ablation procedure through the end of the study or early discontinuation) and all SAEs (time of consent through the end of the study or early discontinuation) will be summarized by MedDRA system organ class and preferred term. A similar summary will also be provided for all SAEs from Visit 3 (the first post-ablation visit) through Visit 6 (end of study) as well as for the entirety of the study (Visit 1 – Visit 6). Ninety-five percent confidence intervals may be provided for pre-specified adverse events of interest, which are:

1. Pneumothorax (overall and CTCAE grade ≥ 2)
2. Hemorrhage, bleeding requiring medical intervention (CTCAE grade ≥ 2)
3. Chest wall pain
4. Pleural effusion or empyema (overall and requiring chest tube drainage)
5. Pneumonia
6. Pulmonary abscess
7. Other lower-tract respiratory infection

8. Bronchopleural fistula.

The Numeric Pain Rating Scale scores will be summarized with methodology consistent to the recommendations of the specific survey. Additional endpoints will be summarized with descriptive statistics.

Plans for Interim Analysis

There are no plans for any formal interim analyses with intent to stop the study early or to modify the study design. However, non-formal interim analyses are planned. The first interim analysis will occur after 20 subjects complete Visit 3 (30 days) and will be descriptive in nature only and will not impact the final analysis. The second interim analysis will occur after all subjects complete Visit 3 (30 days) and will include an evaluation of the primary endpoint against the performance goal as well as provide a summary of all baseline and procedural-related data. A complete summary of all safety-related data observed through the duration of follow-up on all subjects will also be provided. The intent of this analysis will be to support regulatory filing activities where appropriate.

An additional interim analysis may be performed after all subjects have completed Visit 5 (6 months). The final analysis will be completed once all subjects have completed Visit 6 (12 months) and will summarize all endpoints collected during the trial.

Complete details for all planned analyses will be included in the study SAP, which will be finalized prior to database lock.

Analysis of Safety

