## **4 Interval Windows**

Interval windows are provided in Table 1: Schedule of Assessments. No additional windows are planned for analysis purposes.

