## 8.11 Safety Analyses

Perioperative AEs are defined as AEs that occur from the time of subject consent through 30-days post any ablation procedure (i.e., the original ablation as well as any re-ablation) regardless of relationship to the study device or procedure.

Device-/procedure- related AEs are defined as AEs that are deemed related to the study device or procedure 30-days post any ablation procedure (i.e., the original ablation as well as any re-ablation) through the end of the study or early discontinuation.

Serious adverse events (SAEs) will be captured from the time of subject consent through the end of the study or early discontinuation regardless of relationship to the study device or procedure.

The number and percentage of subjects experiencing perioperative AEs, device- and procedure-related AEs, and all SAEs will be summarized by MedDRA system organ class and preferred term. A similar summary will also be provided for all SAEs from Visit 3 (the first post-ablation visit) through Visit 6 (end of study) as well as for the entirety of the study (Visit 1 – Visit 6).

Ninety-five percent confidence intervals may be provided for pre-specified adverse events of interest, which are:

1. Pneumothorax (overall and CTCAE grade  $\geq 2$ )
2. Hemorrhage, bleeding requiring medical intervention (CTCAE grade  $\geq 2$ )
3. Chest wall pain
4. Pleural effusion or emphysema (overall and requiring chest tube drainage)
5. Pneumonia
6. Pulmonary abscess
7. Other lower-tract respiratory infection
8. Bronchopleural fistula.

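### The late SAE table starts at Visit 3 (day 23 to 44) while the perioperative window ends at day 30, and the only scheduled 30-day readmission check can fall before day 30

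*SAP*

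**What the plan says.** **Late SAE table.** SAP 8.11: "A similar summary will also be provided for all SAEs from Visit 3 (the first post-ablation visit) through Visit 6 (end of study". The same sentence adds a table for the whole study. Protocol 10.9 has the same boundary: "all SAEs from Visit 3 (the first post-ablation visit) through Visit 6 (end of study".

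**Perioperative window.** SAP 8.11 defines perioperative AEs as "AEs that occur from the time of subject consent through 30-days post any ablation procedure", whatever their relationship to device or procedure.

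**Date of Visit 3.** Protocol 7.3: "Visit 3 occurs 30 days (-7 to +14 days) after the ablation procedure". SAP 4 adds: "No additional windows are planned for analysis purposes". Protocol 10.4 says the same, so nothing else fixes the start of the late table.

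**SAE capture.** SAP 8.11: "Serious adverse events (SAEs) will be captured from the time of subject consent through the end of the study or early discontinuation". Protocol 7.4 to 7.7 also tell sites to go on recording events that fell within 30 days of an ablation or re-ablation.

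**Readmission.** Protocol 4.4 and SAP 8.9 define the endpoint as unplanned admission due to an adverse event within 30 days of ablation. Protocol 7.3 gives the collection instruction: "Record readmission to any hospital for any unplanned reason within 30 days of the ablation". Table 1 in both documents marks the readmission check at Visit 3 only, and Protocol 7.4 to 7.7 contain no readmission item. Note 20 to the protocol's Table 1 extends the 30 days to any ablation, including a re-ablation.

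**The concern.** Two clocks are in use. One closes at a fixed day after ablation; the other opens at a visit whose date may vary over 22 days. A reader who compares early with late SAE rates in a single-arm study would assume a common boundary, and here the boundary differs between subjects. A subject who never attends Visit 3 has no start date for the late table at all. Safety is part of the primary objective, and under SAP 8.12 the safety summary made after all subjects complete Visit 3 is meant to support regulatory filing.

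For readmission, the endpoint window and the collection schedule do not match. A subject seen on day 23 is asked while a week of the window is still to run. Protocol 6.1 allows re-ablation of a target tumor only after the Visit 3 assessment, so that single check cannot cover the re-ablation readmissions that note 20 asks for.

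**Working it through.** The plan states no figure of its own here. The check is day arithmetic.

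**Inputs**
- Visit 3 day *v* (Protocol 7.3): from 30 − 7 = 23 to 30 + 14 = 44, which is 22 possible days.
- Perioperative window (SAP 8.11): onset day *d* ≤ 30 after the index ablation.
- Late table (SAP 8.11), read by onset date: *d* ≥ *v*. The documents do not state this reading; it is an assumption.
- Readmission window (SAP 8.9): *d* ≤ 30, with one check on day *v*.

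**Formulas**
- Days in both tables: max(0, 30 − *v* + 1).
- Days in neither table: max(0, *v* − 31).
- Readmission days after the only check: max(0, 30 − *v*).

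| Visit 3 on day | In both | In neither | Readmission days after the check |
|---|---|---|---|
| 23 | 8 (23–30) | 0 | 7 (24–30) |
| 26 | 5 (26–30) | 0 | 4 (27–30) |
| 30 | 1 (30) | 0 | 0 |
| 31 | 0 | 0 | 0 |
| 37 | 0 | 6 (31–36) | 0 |
| 44 | 0 | 13 (31–43) | 0 |

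Only day 31, one of the 22 permitted days, gives a clean split. The target day itself overlaps by one day. A late Visit 3 leaves no readmission day unchecked after the index ablation.

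**Averages, if Visit 3 dates were spread evenly over the window.** This is an assumption; the documents give no distribution.
- Both tables: (8 + 7 + … + 1)/22 = 36/22 = 1.6 days per subject.
- Neither table: (1 + 2 + … + 13)/22 = 91/22 = 4.1 days.
- Unchecked readmission time: (7 + 6 + … + 1)/22 = 28/22 = 1.3 days.
- Subjects checked before day 30: 7/22 = 32%.
- Unchecked share of all 30-day readmission time: 28/(22 × 30) = 4.2%.

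**After the change.** With the late table starting at *d* ≥ 31, no day falls in both tables and none in neither, relative to the index ablation and whatever the value of *v*. Some overlap after a re-ablation remains, because the perioperative period restarts with any ablation.

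**The case against.** The strongest reply is that little of consequence follows, and much of it stands.

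- **SAEs are not lost.** They are captured to the end of the study and appear in the all-SAE and whole-study tables. Related ones may also appear in the device- and procedure-related table.
- **The tables are not said to partition follow-up.** The perioperative table covers all AEs, serious or not. The all-SAE table overlaps it by design, and no document adds the tables together. Overlap therefore means that an event is shown in two tables, not that a total is inflated.
- **The wording allows another reading.** The same sentence of the SAP describes the whole study by its visit numbers, so the visits may be labels for when events were collected. On that reading the 13-day gap disappears. However, at Visit 3 sites record events since the last visit, so SAEs between discharge and day 30 would then enter the late table as well as the perioperative one. The boundary needs a definition under either reading.
- **Readmission has a second source.** Hospitalization is an SAE criterion (Protocol 12.1), SAEs are reportable within 72 hours of awareness (Protocol 12.2), and later visits still collect events from the 30-day window.

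A reader might infer that readmission is cut at Visit 3, that readmissions are missed, or that the readmission rate is biased downward. The documents do not support this. The endpoint is tied to 30 days, and an AE-related admission after an early Visit 3 should still be on the SAE record. Nor is the 4.2% a share of missed events: it is unchecked time on one item, under an assumed spread of visit dates.

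**Conclusion.** The point holds in limited form. The late SAE table has a start that differs between subjects: 0 to 8 days in both tables and 0 to 13 days in neither, on an onset-date reading at the actual visit. The larger figures in each range apply only at the edges of the visit window. The 30-day readmission endpoint has a single scheduled check, which can come up to 7 days before its window closes and comes before any re-ablation of a target tumor. AE-related admissions in those periods risk omission from the readmission item, not from the data.

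The effect is confined to one descriptive safety table and one exploratory endpoint. The primary test is unaffected. The 32% and 4.2% figures rest on evenly spread visit dates and should be quoted only with that label. The change is still worth making, because Protocol 7.3 to 7.7 already sort events by 30 days from ablation, and the Visit 3 boundary is the exception.

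**What to change.** 1. **SAP 8.11 and Protocol 10.9.** Start the late SAE table at day 31 after the index ablation, by onset date, in place of Visit 3. State how SAEs within 30 days of a re-ablation are shown, since they are perioperative and late at once. Cost: one or two sentences and table programming, on data already collected.

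2. **SAP 8.9.** Derive readmission from the readmission item plus SAEs that meet the hospitalization criterion within 30 days of the ablation, and state that re-ablations are handled as note 20 to Table 1 requires. The SAE criterion also includes prolongation of a stay, which is not a readmission and must be separated out. Cost: SAP wording and programming.

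3. **If the eCRF holds no admission date.** Protocol 12.2 lists onset and resolution dates but no admission date, and onset may precede admission. In that case, ask the readmission question again at the next visit when Visit 3 was before day 30 or a re-ablation has taken place. Cost: one repeated CRF question and a small change to the schedule.

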## 8.12 Plans for Interim Analysis

There are no plans for any formal interim analyses with intent to stop the study early or to modify the study design. However, non-formal interim analyses are planned. The first interim analysis will occur after 20 subjects complete Visit 3 (30 days) and will be descriptive in nature only and will not impact the final analysis. The second interim analysis will occur after all subjects complete Visit 3 (30 days) and will include an evaluation of the primary endpoint against the performance goal as well as provide a summary of all baseline and procedural-related data. A complete summary of all safety-related data observed through the duration of follow-up on all subjects will also be provided. The intent of this analysis will be to support regulatory filing activities where appropriate.

An additional interim analysis may be performed after all subjects have completed Visit 5 (6 months). The final analysis will be completed once all subjects have completed Visit 6 (12 months) and will summarize all endpoints collected during the trial.

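### The filing-support safety summary specifies only crude percentages although follow-up at that cut runs from about 1 to 12 months, so late-event figures fall below 12-month risk

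*SAP*

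**What the plan says.** SAP 8.12 sets the timing: "The second interim analysis will occur after all subjects complete Visit 3 (30 days"), with the primary endpoint evaluated at the same cut. On safety it adds that "A complete summary of all safety-related data observed through the duration of follow-up on all subjects will also be provided". Protocol 10.9 has the same plan and states the purpose: "The intent of this analysis will be to support regulatory filing activities where appropriate".

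SAP 8.11 defines the statistic: "The number and percentage of subjects experiencing perioperative AEs, device- and procedure-related AEs, and all SAEs will be summarized by MedDRA system organ class", with a further breakdown at preferred-term level. Confidence intervals are optional and limited to a list of adverse events of interest. Two of the categories run to the end of the study. For the first, "Serious adverse events (SAEs) will be captured from the time of subject consent through the end of the study or early discontinuation". The second, late related AEs, starts 30 days after any ablation. SAP 8.11 also asks for an SAE summary over the interval from Visit 3 to Visit 6.

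The Protocol Summary anticipates 2 years of enrollment and 1 year of follow-up. SAP 8.8.2 reserves Kaplan-Meier for LTPFS, PFS, DSS and OS. Neither document gives a person-time rate, a number at risk, a cumulative incidence or a fixed-time denominator for SAEs or late related AEs.

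**The concern.** When the last subject reaches Visit 3, the first subjects have finished 12 months and the last have about one. A percentage of all ablated subjects then mixes very different exposure times. It is not a 30-day risk, because early subjects contribute later events. It is not a 12-month risk, because late subjects have not yet had the time in which such events would occur.

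This analysis is the one meant for filing. A reader who takes the late-event percentage as the device's 12-month safety profile will see a figure that is too low, and cannot correct it without the follow-up distribution. Once all subjects have been ablated the denominator is fixed, so the cumulative percentage cannot fall afterwards and rises with each new first event. An increase between the filing and the final report would therefore not mean that the risk had changed.

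**Working it through.** **The plan's own figures.** The documents state no SAE or AE rate for this study, so there is no safety figure to reproduce. The sample size is used below only to turn percentages into subjects. It reproduces: [(1.960 × √(0.8 × 0.2) + 1.282 × √(0.9 × 0.1)) / 0.1]² = 11.685² = 136.5, so 137; 137 / 0.95 = 144.2, so 145.

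**Inputs from the documents.** Enrollment 24 months (Protocol Summary); follow-up 12 months (SAP 1); cut when the last subject completes Visit 3 (SAP 8.12).

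**Assumptions.** The cut is 1 month after the last ablation. There is no dropout. The first-month risk is p0. The hazard after month 1 is constant, giving a month 1-12 risk of q. The accrual pattern is uniform, linearly rising or linearly falling.

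**Follow-up at the cut.** Let s be the time from a subject's ablation to the end of accrual. Follow-up is f = 1 + min(11, s), and the share of late time observed is E[min(11, s)] / 11.

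- Uniform: E = 121/48 + 11 × 13/24 = 2.521 + 5.958 = 8.479. Mean follow-up is 9.5 months and the late share is 8.479/11 = 0.77. The full 12 months are complete in 13/24 = 54%; 5/24 = 21% have under 6 months and 2/24 = 8% under 3.
- Rising: E = (2/576)(12 × 121 − 1331/3) + 11 × 169/576 = 3.501 + 3.227 = 6.729. Mean 7.7 months, late share 0.61, complete 169/576 = 29%.
- Falling: E = 2 × 1331/(3 × 576) + 11 × (1 − 121/576) = 1.541 + 8.689 = 10.230. Mean 11.2 months, late share 0.93, complete 79%.

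**Late events.** The expected crude percentage is the mean of 1 − exp(−λ(f − 1)), with λ = −ln(1 − q)/11. Under uniform accrual this equals (13/24)q + (11/24)[1 − q/(−ln(1 − q))]. For q = 0.20 it is 0.1083 + (11/24)(1 − 0.8963) = 0.1083 + 0.0475 = 0.156, a ratio of 0.78. Over q from 2% to 30% the ratio is 0.77-0.78 (uniform) and 0.61-0.63 (rising). Under falling accrual it is about 0.93. For q = 10%, uniform, the crude figure is 7.8%.

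**All SAEs.** The crude percentage is 1 − (1 − p0)(1 − crude late percentage); the 12-month value is 1 − (1 − p0)(1 − q).

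| p0 | q | 12-month | Crude, uniform | Ratio | Crude, rising | Ratio |
|---|---|---|---|---|---|---|
| 5% | 2% | 6.9% | 6.5% | 0.94 | 6.2% | 0.89 |
| 5% | 20% | 24.0% | 19.8% | 0.83 | 16.9% | 0.70 |
| 5% | 30% | 33.5% | 27.4% | 0.82 | 23.0% | 0.69 |
| 10% | 2% | 11.8% | 11.4% | 0.97 | 11.1% | 0.94 |
| 10% | 30% | 37.0% | 31.2% | 0.84 | 27.1% | 0.73 |

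In the second row, with 145 subjects, uniform accrual gives 28.7 subjects at the cut against 34.8 at 12 months. A first-month risk of 15% moves only the upper ends of the ranges. With q = 2%, uniform accrual gives 1 − 0.85 × (1 − 0.0154) = 0.163 against 0.167, a ratio of 0.98. Rising accrual gives 1 − 0.85 × (1 − 0.0123) = 0.160, a ratio of 0.96.

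**Does a censored estimate remove the shortfall?** In 4,000 simulated trials of 145 subjects (p0 = 5%, q = 20%, uniform accrual), the crude percentage at the cut averaged 19.7%. On the same data, 1 − Kaplan-Meier at 12 months averaged 24.0%, equal to the final percentage. The final figure exceeded the interim crude figure in 99.8% of runs and was never lower.

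**The case against.** The strongest defence is that nothing is misreported. SAP 8.12 speaks of data observed so far and never calls the result a 12-month risk. As a tally to the cut it is accurate. That stands: the shortfall exists only against 12-month risk. But SAP 8.11 frames these categories as running to the end of the study, so a reader is likely to take them that way.

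No inference depends on the summary. The only hypothesis concerns Technique Efficacy, there is no safety performance goal, and the interim is called non-formal. That also stands: the primary endpoint, alpha and sample size are untouched.

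The window of most procedural interest is nearly complete. Everyone has had Visit 3, so events within 30 days of the original ablation are almost fully observed, except after a Visit 3 as early as day 23. Events after late re-ablations are also still to come. Deaths are covered by Kaplan-Meier through OS and DSS, and disease progression is not reported as an SAE. These points narrow the concern to late related AEs and late SAEs.

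Four stronger readings are tempting but not supported.

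- A reader might infer that SAP 8.13 forbids adjusting for incomplete follow-up. It rules out imputation; censored and person-time estimates are not imputation. On safety it is silent.
- A reader might take the Visit 3 to Visit 6 SAE table as the worst case at filing. SAP 8.12 does not say which tables appear at the interim, and that table fits the final analysis most naturally. Nor do the documents say that subjects who have not reached a window stay in its denominator; this is the natural reading only because no other denominator is given.
- A reader might use a 30% 12-month SAE risk at constant hazard from day 0, which gives 24% against 30% under uniform accrual. That leaves out any procedural peak, and the documents supply no such rate.
- A reader might extend the point to the final analysis through dropout and deaths. The documents give no 12-month dropout figure from which to size it.

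**Conclusion.** The concern holds as a gap in the interim safety specification. At the filing-support cut the plan names only crude percentages, follow-up differs by up to about 11 months between subjects, and nothing in SAP 8.11 to 8.13 accounts for it. The late-event percentages will lie below 12-month risk as long as any first events remain to occur.

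The size depends on how subjects accrue and when events occur. Late events show about 0.77 of their 12-month value under uniform accrual, 0.61 under rising and 0.93 under falling accrual. For all SAEs the shortfall is smaller, because the first month is fully observed: 0.82-0.97 (uniform) or 0.69-0.94 (rising) with a first-month risk of 5-10% and a later risk of 2-30%. The direction is firm. The sizes are illustrations that rest on the assumed accrual, a constant late hazard and no dropout. This is a worthwhile, inexpensive improvement and does not threaten the trial's main conclusion.

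**What to change.** In SAP 8.11 and 8.12, for SAEs and for related AEs after day 30, add one of the following to the second interim and to any later analysis with incomplete follow-up:

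- a time-to-first-event cumulative incidence with 95% CI and numbers at risk, by Kaplan-Meier or by Aalen-Johansen with death as a competing event. Report it at day 30 and month 12 for SAEs. For late related AEs, report it at month 12 with time at risk starting at day 30, since the day-30 value is zero by definition;
- or, as the simpler choice, an events-per-patient-year rate.

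Show the distribution of follow-up at the cut and label every crude percentage with the data-cut date. State the denominator and say which SAP 8.11 tables appear at the second interim. Keep crude percentages as the main figure for the 30-day window.

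The optional 6-month interim needs the same treatment, though less acutely. Under uniform accrual with that cut 6 months after the last ablation, 18/24 = 75% of subjects would have the full 12 months, and mean follow-up would be 0.75 × 12 + 0.25 × 9 = 11.25 months.

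The cost is SAP wording and one extra table per category. The ablation and event onset dates are already recorded. The late-event rates quoted at filing will look less favourable, and the month-12 estimate will be less precise because fewer subjects have reached that point.
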